5.6 Prior and Concomitant Medications and/or Procedures

5.6.1 Permitted Medications and/or Procedures

During the course of the clinical study, subjects are anticipated to continue the use of prescribed medications identified during the screening procedures, consistent with study inclusion and exclusion criteria. Permitted concomitant medications used in this study include:

- 7-day antibiotic regimen scheduled 7 days after the last dose of CRS-207 ([Section 5.6.3](#))
- Acetaminophen (paracetamol; ibuprofen if allergic to acetaminophen) prior to each CRS-207 infusion (no more than 4 g/d of acetaminophen)
- Antipyretics to treat fever or to prevent recurrence of fever
- Antiemetics according to American Society for Clinical Oncology guidelines.⁶³ If daily administration of an antiemetic is required, an alternative to dexamethasone should be used.
- IV narcotics such as morphine (per institutional policy) for rigors associated with CRS-207 dosing (use of meperidine is prohibited per protocol).

- Palliative (limited-field) radiation therapy is permitted for all anatomic sites except lung, but only for pain control to sites present at baseline and with approval by the Study Medical Monitor.

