10.2.1.2 Progression-Free Survival

PFS is defined as the time from the date of first dose to PD or death due to any cause. Subjects who do not experience PD and do not die on or before the data cut-off date will be censored at the time of last tumor assessment or data cut-off date, whichever is earlier. Subjects who do not experience PD and start new systemic therapy will be censored at the time the new systemic therapy was begun or the data cut-off date, whichever is earlier. Subjects with no assessments of PD will be censored at the time of first dose. Subjects who are lost to follow up for assessment of PD will be censored at their last tumor assessment or data cut-off date whichever is earlier. Kaplan-Meier methodology will be used to estimate median PFS for each cohort in Phase 1 and in each Arm in Phase 2.

The primary definition of PD for PFS is based on mRECIST. Analyses will be performed separately using objective disease responses definitions based on the mRECIST, RECIST v1.1, and GCIG CA-125 criteria. Analysis repeated for RECIST v1.1 and GCIG CA-125 are considered supportive.

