| 
 • Assess safety of CRS-207/pembrolizumab administered with or without epacadostat • Assess tumor response and PFS | 
 • Adverse events, vital signs, physical exam findings, changes in ECG readings, and changes in chemistry, hematology, and coagulation parameters • ORR, defined as CR or PR as determined by mRECIST • PFS, defined as the time from the date of first dose to PD or death due to any cause. PFS is measured through the last tumor assessment or commencement of a new systemic therapy. PD is determined by |

| | |
|--|--|
| | mRECIST. |
| Secondary | |
| 
 • Assess disease control rate and duration of response • Assess OS | 
 • Disease control rate, defined as CR+PR+SD as determined by mRECIST, RECIST v1.1, and GCIG CA-125 criteria • Duration of response, defined as the time from first CR or PR until PD as determined by mRECIST, RECIST v1.1, and GCIG CA-125 criteria • ORR as determined by RECIST v1.1 and GCIG CA-125 criteria • OS, defined as the time from first dose until date of death due to any cause • PFS where PD is determined by RECIST v1.1 and GCIG CA-125 criteria |
| Additional | |
| 
 • *Assess the association of clinical efficacy (ORR, PFS, and OS) with immunologic and tumor biomarkers • *Characterize the PK of epacadostat • *Characterize shedding and clearance of CRS-207/pembrolizumab administered with or without epacadostat | 
Immunological and tumor biomarker endpoints:
 
 • Cytokine/chemokine and antibody responses • Modulation of immune cell populations and functions in PBMCs and tumor • Mesothelin, IDO-1 and PD-L1 expression • CA-125 and additional candidate tumor biomarkers 
Pharmacokinetic endpoints:
 
 • Plasma concentration of epacadostat and derived PK parameters • Detection of CRS-207 in urine, saliva, feces, and blood |

This ASAP provided derivation and listing of the efficacy endpoint, however no summary tables will be produced for these endpoints. The derivation and analysis of selected immunological/ biomarker endpoints and PK parameters will be discussed in another standalone document(s).

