5.6. Imputation of Partial Dates

Adverse Events and Concomitant Medications

- If the AE start date is completely missing, no imputation will be conducted.
- If the AE start date is missing day and month, do the following:
 - If the treatment start date is missing or the AE year does not fall in the same as that of first treatment or if the AE contains information to indicate that the event ended before the date of first study treatment (e.g. AE end date month and year are earlier than the treatment start date or the full date is known and occurs earlier than the date of first treatment), then set the start month and day to January 1st
 - Otherwise, set the start date to the date of first study treatment
- If only the day is missing, do the following:
 - If the study treatment start date is missing or the month and year does not fall in the same as that of first treatment or if the AE contains information to indicate that the event ended before the date of first study treatment, then set the start month and day to the 1st of the stated month
 - Otherwise, set the start date to the date of first study treatment
- End dates will not be imputed

Subsequent Anticancer Therapy, Radiotherapy or Anticancer Surgical Procedures

Partial dates for subsequent therapies will not typically be imputed, but may be needed to support efficacy outcome derivations (e.g. PFS censoring dates). In this case, the following will be applied for imputation of new anti-cancer therapies taken after first study treatment:

- If the start date is completely missing, no imputation will be conducted
- If the start date is missing day and month, do the following:
 - If progressive disease (PD) has been identified in the year noted, new anti-cancer therapy date will be assigned to begin one day after the date of PD.
 - Otherwise the new anti-cancer therapy date will be assigned to January 1st.
- If only the day is missing, do the following:

Sponsor: Aduro Biotech, Inc.
Protocol Number: ADU-CL-11
Version and Date: Version 1.0, 03MAY2018

- If PD has been identified in the year noted, new anti-cancer therapy date will be assigned to begin one day after the date of PD.
- Otherwise the new anti-cancer therapy date will be assigned to the 1st of the stated month.

Overall Response Date

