6.7. Anticancer Therapies

Anticancer therapies will be coded to ATC and preferred name based on the WHO Drug Dictionary (WHO-DDE B2, March 2016). It is assumed that these therapies will be collected on the associated CRF have been taken following study drug discontinuation in compliance with the protocol. Anticancer therapies will be presented in a data listing.

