The first date of objectively determined progressive disease would be the earliest date of any post-baseline overall response finding of progressive disease is confirmed as part of the tumor lesion assessment data or death, unless a subject is censored at an earlier date. If an assessment occurs over several days, the method described in Section 5.6 will be used. If there are no adequate assessments for a subject, they will be censored on their first dose date unless they died prior to having their first assessment (in which case they will be considered to have had a PFS event of death). If a subject receives subsequent anticancer therapy prior to documentation of

Sponsor: Aduro Biotech, Inc.
Protocol Number: ADU-CL-11
Version and Date: Version 1.0, 03MAY2018

progressive disease, PFS will be censored at the latest adequate assessment prior to therapy initiation.

Subjects who progress or die following an extended period of follow up will also be censored at a latest adequate assessment prior to the end of a predefined lapse window, even if information is available regarding progression or death after this extended period. Should a subject die after the end of this lapse window they will be censored at their first dose date. The lapse window after which PFS events will not be considered is defined in Section 5.7.

If a subject does not receive confirmation of radiologically identified PD, and there are no further assessments prior to censoring, the subject will be considered to have progressed based on their last valid assessment.

Otherwise, if a subject does not have documented progression, the subject will be censored at the latest adequate assessment.

PFS will be listed for each subject.

Disease Control Rate

Disease control rate (DCR) is defined as the number of subjects who exhibit a BOR response of CR, PR or SD divided by the number of evaluable subjects.

The derivation analysis of DCR will be produced based on mRECIST, RECIST 1.1, and GCIG CA-125 criteria. A description of BOR derivations for RECIST 1.1 and GCIG CA-125 can be found in a previous section.

DCR will not be reported in the CSR synopsis. BOR will be listed for each subject.

Duration of Response

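### SAP 7.1 and 5.6 widen the PFS censoring trigger from new systemic therapy to any subsequent anticancer therapy, undeclared, and leave it unclear whether permitted palliative radiotherapy censors PFS

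*SAP*

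**What the plan says.** Protocol 10.2.1.2 gives one therapy-related reason for censoring: "Subjects who do not experience PD and start new systemic therapy will be censored at the time the new systemic therapy was begun", or at the data cut-off if that is earlier. The endpoint tables in SAP Section 2 keep this for both phases: "PFS is measured through the last tumor assessment or commencement of a new systemic therapy".

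The derivation in SAP 7.1 reads differently: "If a subject receives subsequent anticancer therapy prior to documentation of" "progressive disease, PFS will be censored at the latest adequate assessment prior to therapy initiation". The word systemic is gone, and the censoring date moves back from the start of the therapy to the last adequate scan. SAP 7.1 also drops scans made after a switch to another anticancer therapy, ends the window for best overall response (BOR) at new cancer treatment, and applies similar censoring to duration of response (DOR).

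SAP 5.6 has a partial-date rule headed "Subsequent Anticancer Therapy, Radiotherapy or Anticancer Surgical Procedures". It says that these dates "may be needed to support efficacy outcome derivations (e.g. PFS censoring dates"), and it covers therapies taken after first study treatment.

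Protocol 5.6.1 lists a radiotherapy that a conforming subject may have while on study: "Palliative (limited-field) radiation therapy is permitted for all anatomic sites except lung, but only for pain control to sites present at baseline", with Medical Monitor approval. SAP Section 9 declares one change only: efficacy endpoints are derived and listed but not summarized.

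**The concern.** The SAP contradicts the protocol and its own Section 2 on what censors a Phase 2 primary endpoint, and does not say so. A programmer who follows 7.1 and 5.6 together has grounds to count radiotherapy and surgery as triggers. One who follows Section 2 does not.

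The case that matters is a subject who has permitted palliative radiotherapy, stays on treatment and progresses later. Under the protocol her progression is an event. Under the literal SAP wording it is not, and her later scans do not count towards BOR. If radiotherapy for pain tends to come shortly before documented progression, such censoring is informative, and the loss of events would lift any Kaplan-Meier median estimated from the data.

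**Working it through.** **The rules side by side**

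| Place | Trigger | Date used |
|---|---|---|
| Protocol 10.2.1.2 | New systemic therapy | Start of therapy, or data cut-off if earlier |
| SAP 2, Phases 1 and 2 | New systemic therapy | Commencement of therapy |
| SAP 7.1 | Subsequent anticancer therapy | Last adequate assessment before it |
| SAP 5.6 | Heading names anticancer therapy, radiotherapy and surgery | Fills in partial dates |

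Both the trigger and the date have changed.

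**A worked record.** Assume stable disease at the first 9-week scan (9 × 7 = Day 63), palliative radiotherapy on Day 90, progression at the second scan (18 × 7 = Day 126), and no systemic therapy.

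- Protocol: event on Day 126 (126/7 = 18.0 weeks).
- SAP 7.1, radiotherapy counted: censored on Day 63 (63/7 = 9.0 weeks). The listed time gets shorter; what is lost is the event.
- SAP 7.1 and 5.6, radiotherapy counted but its day missing, progression in the same year: 5.6 sets the therapy to the day after progression (Day 127), so the event on Day 126 stands. The result then depends on how complete the date is.
- Had the Day 90 therapy been systemic, both documents would censor, on Day 90 and Day 63 respectively, 27 days apart.

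**The plan's own PFS figure.** The inputs are in protocol 10.2.4 and SAP 3.3: 27 subjects accrued over 24 months, 30 months in total, exponential PFS, null median 3.6 months, threshold 4.8 months. With L = ln 2 / 3.6 = 0.1925, expected events are d = 27 × [1 − (e^(−6L) − e^(−30L)) / (24L)] = 25.18. Then 1 − Φ(ln(4.8/3.6) × √25.18) = 0.0744, as stated. The same formula gives power of 0.770 at 5.6 months and 0.500 at 4.8 months, also as stated.

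**Possible effect on a later median.** This is a simulation of 4,000 trials per setting with the inputs above and a true median of 3.6 months. The documents give no radiotherapy rate or timing, so both are assumed. *Linked* places radiotherapy in the 1.5 months before progression is detected. *Independent* gives it a constant hazard unrelated to progression, set so that about the stated share have it before progression. The entries are the chance that the Kaplan-Meier median is at least 4.8 months.

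| Scans | Share irradiated | Not a trigger | Trigger, linked | Trigger, independent |
|---|---|---|---|---|
| Continuous | 5% | 0.13 | 0.18 | 0.15 |
| Continuous | 10% | 0.13–0.14 | 0.24 | 0.14 |
| Continuous | 20% | 0.13–0.14 | 0.37 | 0.16 |
| 9-weekly | 5% | 0.30–0.31 | 0.35 | 0.29 |
| 9-weekly | 10% | 0.30–0.31 | 0.42 | 0.29 |
| 9-weekly | 20% | 0.29–0.30 | 0.55 | 0.30 |

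The Monte Carlo error is about √(0.3 × 0.7/4000) = 0.007. With continuous assessment the typical estimated median rises from about 3.6 to 3.75, 3.94 and 4.36 months when linked, and stays at 3.60 to 3.66 when independent.

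The *not a trigger* column lies above 0.0744 for reasons unrelated to this point. The plan's figure rests on an exponential-model median, and scans every 63/30.4375 = 2.07 months allow observed medians only at 2.07, 4.14, 6.21 months and so on.

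**The case against.** The strongest reply is that nothing in the SAP says on-study palliative radiotherapy censors PFS. SAP 6.7 codes anticancer therapies as drugs and assumes they "have been taken following study drug discontinuation in compliance with the protocol". The word *switch* in 7.1 suggests a replacement treatment, which a permitted concomitant measure is not. SAP 5.6 fills in partial dates and does not define a trigger. Nor is loose wording peculiar to the SAP: protocol 8.1.2 stops imaging at new anticancer treatment, also without the word systemic. If palliative radiotherapy counted there, the later scan in the worked record might never be made.

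Much of this stands. It makes the treatment of palliative radiotherapy ambiguous, not settled. It does not remove the contradiction: the operative sentence in 7.1 says receives, no passage exempts palliative radiotherapy, 6.7 governs coding and listing, and the imaging rule in 8.1.2 is not the protocol's censoring rule.

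The second reply is also sound. A reader might infer that PFS in this trial is overstated. The documents do not support that. Under SAP 2 and 9 efficacy is only listed, so no median is compared with 4.8 months. Upward bias also needs radiotherapy to be linked to imminent progression, which no passage shows, and protocol 5.6.1 restricts its use. The underlying scans and later therapies remain visible in their own listings.

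**Conclusion.** The point holds as an undeclared contradiction in the censoring rule for a primary endpoint, with an ambiguity over permitted palliative radiotherapy. It should be corrected.

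Under this SAP the direct effect is on individual records: the PFS and DOR time and censor flag, and BOR. In the example, an event on Day 126 becomes a censored time on Day 63. That rests on the literal reading of 7.1 with 5.6.

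For a median estimated later, the effect runs from essentially none (independent timing) to a rise in the chance of passing 4.8 months from about 0.30 to between 0.35 and 0.55 (linked timing, 9-weekly scans, 5% to 20% irradiated). These are conditional illustrations on assumed rates and timing, not estimates for this trial. It is not established that permitted radiotherapy is meant to censor, or that PFS is overstated.

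**What to change.** 1. In SAP 7.1 and 5.6, make new systemic therapy the cut-off for PFS, DOR and BOR, as in protocol 10.2.1.2 and SAP Section 2.
2. State that palliative radiotherapy permitted under protocol 5.6.1 neither censors PFS nor excludes later assessments.
3. Record in SAP Section 9 any departure that is intended, in the trigger or in the censoring date (therapy start in the protocol, last adequate assessment in the SAP).

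The cost is a few sentences and a filter on therapy type. The downside is that a target lesion that has been irradiated or resected can shrink or vanish for reasons other than study treatment, so such lesions must be flagged and read with care. A sensitivity listing that censors at any anticancer therapy can be kept, and would show which records depend on the choice.

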5.7. Lost to Follow Up or Lapse of Adequate Assessments

If a subject has missed two or more scheduled disease assessments, a censoring date will be required in support of relevant survival endpoint derivations. For example, PFS will be censored at the last adequate disease assessment prior to the lost to follow up window. However, this survival outcome would be considered censored after an extended amount of time without additional assessment (after two have been missed). Based on a protocol specified disease assessment schedule of every 9 weeks, a window of 140 days [18 weeks + 14 days] would be used as the censoring date (assuming a protocol window period of 7 days for each assessment).

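### SAP 7.1 censors a death after the lapse window at the first dose date, against the sentence before it, SAP 5.7 and the protocol, so a subject with clean scans is listed with a PFS of 1 day

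*SAP*

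**What the plan says.** SAP 7.1 (Progression-Free Survival) deals with progression or death after a long gap in scans. Such subjects are "censored at a latest adequate assessment prior to the end of a predefined lapse window, even if information is available regarding progression or death" after that gap. The next sentence then says: "Should a subject die after the end of this lapse window they will be censored at their first dose date".

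A few lines earlier, the same section covers subjects with nothing to assess: "If there are no adequate assessments for a subject, they will be censored on their first dose date unless they died" before a first assessment was made, in which case the death counts as a PFS event.

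SAP 5.7 sets the lapse at two or more missed assessments. It says "PFS will be censored at the last adequate disease assessment prior to the lost to follow up window", and then that "a window of 140 days [18 weeks + 14 days] would be used as the censoring date".

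Protocol 10.2.1.2 counts progression or death from any cause as the event and has no lapse window. It reserves first-dose censoring for subjects with no assessment of progression. On the remaining case it says: "Subjects who are lost to follow up for assessment of PD will be censored at their last tumor assessment", or at the data cut-off if that is earlier.

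SAP 9 declares one change from the planned analysis: efficacy endpoints are derived and listed but not summarised.

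**The concern.** The first of the two adjacent sentences in SAP 7.1 already covers deaths after the lapse. The second gives the same deaths a different censoring date. A programmer has to choose between them.

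If the second is followed, a subject with several clean scans leaves the risk set on day 1. The trigger is a later death, so the censoring time depends on the outcome. A subject with the same scans who is not known to have died keeps all her observed time.

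The situation can arise in this trial. Subjects who come off treatment go into follow-up where survival is checked every 12 weeks, so a death can be recorded well after the last scan.

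PFS is a Phase 2 primary endpoint and a Phase 1 secondary endpoint. SAP 7.1 repeats the derivation for RECIST 1.1 and GCIG CA-125, so the same sentence would act on all three versions of PFS in the listing.

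**Working it through.** **The SAP's own figure.** The lapse length in SAP 5.7 reproduces: 18 weeks × 7 + 14 days = 140 days.

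**Formula.** SAP 5.3 gives time = event or censoring date − reference date + 1, with months = days / 30.4375. The reference date is first dose. Censoring at first dose therefore always gives 1 day.

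**Example (dates assumed).** First dose is day 1. Scans without progression at weeks 9, 18 and 27, none afterwards, no new therapy, death at month 12.

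- Last adequate scan: 27 × 7 = 189 days after first dose, so time = 190 days, and 190 / 30.4375 = 6.2 months.
- End of lapse: day 190 + 140 = day 330.
- Death: 12 × 30.4375 = about day 365, which is after the lapse.

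| Rule | PFS for this subject |
|---|---|
| SAP 7.1, first sentence | censored at 190 days (6.2 months) |
| SAP 7.1, second sentence | censored at 1 day (0.03 months) |
| SAP 5.7, last adequate assessment | censored at 190 days (6.2 months) |
| Protocol 10.2.1.2, PFS definition | event at about 365 days (12 months) |
| Protocol 10.2.1.2, if lost to follow-up for progression | censored at 190 days (6.2 months) |
| SAP 7.1, same scans but no known death | censored at 190 days (6.2 months) |

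Only the second sentence gives 1 day.

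**Direction.** Moving a subject's censoring from her last scan to day 1 takes her out of the risk set for every event before that scan. Each such event then produces a larger drop in the Kaplan-Meier curve. After the scan date the steps are the same. Compared with last-assessment censoring, the curve can only be lower or equal, and so can its median.

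**Possible size if a median were computed later.** The documents give no count of affected subjects, so 1, 3 and 5 are assumed. The simulation used 27 subjects, exponential PFS with a true median of 4.8 months, uniform accrual over 24 months, 30 months in total and 8,000 repetitions. Affected subjects were drawn from those progression-free for at least two 9-week scans. With no lapses, the chance of an observed median of at least 4.8 months was 0.50, which matches the 50% power stated in Protocol 10.2.4.

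| Affected subjects | Typical median, last-assessment censoring | Typical median, first-dose censoring | Chance of median ≥ 4.8 months, last-assessment | Chance of median ≥ 4.8 months, first-dose |
|---|---|---|---|---|
| 1 | 4.85 | 4.40 | 0.51 | 0.38 |
| 3 | 4.96 | 3.92 | 0.54 | 0.26 |
| 5 | 5.09 | 3.48 | 0.57 | 0.16 |

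These figures show sensitivity. They do not predict this trial's result.

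**The case against.** **Little in this SAP depends on PFS.** This stands. The SAP is abbreviated, written for a synopsis report after development had ceased. Efficacy is listed only, no significance test is done and no figure is planned. A reader might infer that the sentence distorts a planned primary analysis or the 4.8-month decision. The SAP plans no Kaplan-Meier curve, no median and no comparison with 4.8 months. Scans, response assessments and deaths are also listed, so a careful reader could see what lies behind a 1-day value.

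**The sentence may have been meant only for subjects with no adequate scan.** On that reading no observed time is lost, and an intent to discard clean scans is not established. But the text does not state the limit. That reading also meets the rule that a death before the first assessment is an event. If the sentence was meant to restrict that rule to deaths within 140 days of first dose, it has to say so. Either way the wording needs an edit.

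**The protocol counts death as an event.** Correct, and it cuts both ways. First-dose censoring departs from the protocol, but so does the preceding SAP sentence, because the protocol has no lapse window. Deleting the second sentence restores consistency within the SAP but does not by itself restore the protocol's definition.

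**A third value of about 10.8 months.** A reader might take the 140 days in SAP 5.7 as a literal censoring date, giving (190 + 140) / 30.4375 = 10.8 months in the example, and describe the spread as about twice the 4.8-month criterion. That reading is strained, since the same paragraph of SAP 5.7 says censoring is at the last adequate assessment. One subject's spread is also not comparable with a threshold for an arm's median.

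**Duration of response.** A reader might infer that it inherits the error, because SAP 7.1 calls its censoring similar to that for PFS. It runs from first response, so a first-dose date would give a negative duration, which SAP 5.3 excludes. The carry-over is not established.

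**Conclusion.** The point holds as an error in a derivation rule. For one and the same death, two adjacent sentences of SAP 7.1 give different PFS times, and the second conflicts with SAP 5.7 and with Protocol 10.2.1.2. Followed literally, it gives 1 day instead of about 6.2 months in the example.

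The affected output is the PFS listing (Listing 16.2.6.2.6), which is the SAP's only PFS output, and any median later computed from it. The likely direction of such a median is downward, so the error would understate activity. How far depends on how many subjects died after a lapse with clean scans behind them, which the documents do not give. The departure of the lapse rule from the protocol is a separate gap, and SAP 9 does not declare it.

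**What to change.** In SAP 7.1, delete the sentence on deaths after the lapse window. Keep the preceding rule: progression or death after the lapse is censored at the last adequate assessment. Keep first-dose censoring only for subjects with no adequate post-baseline assessment, and leave in place the rule that a death before the first assessment is a PFS event. State whether the lapse window, counted from first dose, limits that rule.

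In SAP 5.7, change the clause on the 140 days from being *used as the censoring date* to being *used to define the lapse*.

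In SAP 9, declare that the lapse rule departs from the protocol, which has no such window and counts death from any cause as an event. Also list PFS under the protocol's definition, so that both values can be seen.

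The cost is a few sentences, minor derivation work and one extra listed value per affected subject.
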